12.8 Notification of Safety Information to Investigators, Regulatory Authorities, and IRBs/IECs

In accordance with the EU Clinical Trials Directive⁶¹, relevant parts of the FDA Code of Federal Regulations⁶³, and any national regulations, GW will inform investigators, regulatory authorities and relevant IRBs/IECs of all relevant safety information. This

EudraCT Number: 2015-004904-50

Protocol V3 20Sep16

will include the reporting of relevant SAEs and all suspected unexpected serious adverse reactions (SUSARs).

This information will be provided through 3 sources:

- 1. IB⁵³: a compilation of the clinical and non-clinical safety data available on the IMP that is relevant to the trial. The IB is updated annually.
- 2. Development core safety information: this document forms the safety section of the IB⁵³, or is updated as an addendum to the IB⁵³. This document is revised if necessary, when new important safety information becomes available (potentially up to a few times a year).
- 3. Council for International Organizations of Medical Sciences (CIOMS) reports: these reports are issued every time a SUSAR is reported to GW. They provide information on individual case reports and are sent to all the regulatory authorities, the relevant central IRBs/IECs which have approved the trial and investigators. As required, the investigator should notify their regional IRBs/IECs of SAEs or SUSARs occurring at their site and other AE reports, i.e., CIOMS reports and any additional safety documentation received from GW, in accordance with local procedures.

In the US, investigators are normally required to report promptly to their IRBs all unanticipated problems involving risks to patients, or others, including AEs that should be considered unanticipated problems. Based on current FDA guidance⁵⁸ the following clarification is provided in determining what constitutes an unanticipated problem:

In general, an AE observed during the conduct of a trial should be considered an unanticipated problem involving risk to patients and reported to the IRB, *only* if it were unexpected, serious, and would have implications for the conduct of the trial (e.g., requiring a significant, and usually safety-related, change in the protocol such as revising inclusion/exclusion criteria or including a new monitoring requirement, informed consent, or IB). An individual AE occurrence *ordinarily* does not meet these criteria because, as an isolated event, its implications for the trial cannot be understood.

The FDA guidance⁶³ states that, accordingly, to satisfy the investigator's obligation to notify the IRB of unanticipated problems, any investigators participating in a multisite trial may rely on the sponsor's assessment and provide to the IRB a report of the unanticipated problem prepared by the sponsor.

EudraCT Number: 2015-004904-50

Protocol V3 20Sep16

GW will inform investigators, regulatory authorities and relevant IRBs/IECs of any safety issues or case reports that are considered to be unanticipated and provide such reports as mentioned above. It should be noted that a single SUSAR report notified to investigators in the trial does not necessarily constitute an unanticipated problem unless identified by GW in the submission cover letter.

As a minimum, the recipient will be sent all of the above and relevant updates between the period from ethical approval and final database lock.

EudraCT Number: 2015-004904-50

Protocol V3 20Sep16

[figure not shown]
13 STATISTICAL CONSIDERATIONS

13.1 Sample Size, Power, and Significance Levels

The pilot phase is not powered and comprises 10 patients. Both cohorts in the pilot phase will comprise 5 patients, the first cohort aged between 6 and 24 months and the second cohort aged between 1 and 24 months, who will all receive GWP42003-P.

The pivotal phase will comprise 192 patients, aged 1–24 months, who will be randomized to receive 1 of 2 dose levels of GWP42003-P (High Dose Level or Low Dose Level) or matching placebo on a 1:1:1 basis (64 per treatment group). Patients in the placebo group will be further split into 2 cohorts (32 patients receiving Low Dose Level dosing volumes and 32 patients receiving High Dose Level dosing volumes), but it is assumed that these 2 cohorts can be pooled for the analyses of efficacy.

Assuming a 20% screen failure rate, it is expected that approximately 245 patients will need to be screened to achieve this target (202 patients included in the pilot and pivotal phases in total).

This is based on a 2-sided 5% significance level, based on a Fisher's exact test.

13.2 Interim Analysis

No formal interim analysis will be conducted. A review of safety and efficacy data will be conducted after the end of the pilot phase, and blinded data review(s) may be conducted to support IMP clinical development. However, for the pivotal phase, it is anticipated that the database will be locked and treatment unblinded, prior to the completion of the OLE phase.

13.3 Analysis Sets

Statistical analysis will be performed according to a statistical analysis plan (SAP). Details of any deviations from the SAP will be documented in the clinical study report.

EudraCT Number: 2015-004904-50

Protocol V3 20Sep16

There will be 3 analysis sets for this trial:

Pilot or Pivotal Phase Safety

All patients exposed to at least 1 dose of IMP during the pilot or pivotal phase will be used for summaries of the safety endpoints during both phases.

OLE Phase Safety

All patients exposed to at least 1 dose of IMP during the OLE phase will be used for summaries of the safety endpoints during the OLE phase.

Intention to Treat (ITT)

All patients in the pivotal phase who are randomized and receive IMP will be included and analyzed according to their randomized treatment group. The ITT analysis set is the primary analysis set for all efficacy endpoints.

13.3.1 Protocol Deviations

Protocol deviations will be listed and reasons for exclusion from the analysis sets will be summarized.

13.4 General Considerations

Unless stated otherwise, continuous variables will be summarized showing the number of non-missing values (n), mean, standard deviation, median, minimum, and maximum. Categorical variables will be summarized showing the number and percentage of patients falling into each category.

13.5 Accountability and Background Characteristics

13.5.1 Enrollment and Disposition

All patients (screened, treated, entering the OLE, prematurely terminating IMP) will be accounted for in the enrollment and disposition summary tables.

13.5.2 Baseline and Demographic Characteristics

Baseline characteristics, including demographics, medical history, and concomitant medications will be summarized by treatment group and overall as appropriate.

13.6 Endpoints and Statistical Methods

For the pivotal phase, only data from this phase will be used for analysis of the primary and secondary endpoints; data from the pilot phase may be used in subsequent sensitivity analyses. Data from all phases will be used for a number of

EudraCT Number: 2015-004904-50

Protocol V3 20Sep16

descriptive summaries for certain endpoints. All safety endpoints for the phases of the trial will be summarized as detailed in Section 13.6.5 below.

For the pivotal phase of the trial, statistical hypothesis testing will be performed on the secondary endpoints as appropriate.

Since there is a single primary analysis endpoint for the pivotal phase, no formal adjustment of statistical significance for multiple testing on multiple endpoints is required, although such multiplicity should be allowed for when interpreting the results for secondary endpoints. However, there are 3 treatments, so multiple significance testing will occur when making comparisons between the treatments; the major comparisons of interest are those between each of the GWP42003-P dose levels and placebo. To control the type I error, a step-up Hochberg's procedure will be used for the primary endpoint of the pivotal phase. If both of the observed p-values from the Low Dose Level and High Dose Level comparisons with placebo are < 0.050 in favor of the GWP42003-P treatment groups, then both groups would be declared statistically significantly better than placebo. However, if the observed p-value is ≥ 0.050 for one GWP42003-P treatment group but < 0.025 in favor of the other GWP42003-P treatment group, then only the latter GWP42003-P treatment group will be declared statistically significantly better than placebo.

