4.1.2 Secondary Endpoint(s)

4.1.2.1 All Phases

The following endpoints will be analyzed separately for each phase:

Key: The number and proportion of patients who are free of clinical spasms, as observed on video-EEG at the end of the treatment period.

Key: The number and proportion of patients who have resolution of hypsarrhythmia as, observed on video-EEG at the end of the treatment period.

Changes in spasms and seizure subtypes by caregiver observation during the treatment period.

Time to cessation of spasms during the treatment period, as determined by caregiver diaries.

Caregiver Global Impression of Change (CGIC).

Physician Global Impression of Change (PGIC).

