13.6.3.2 Pivotal Phase

For the pivotal phase, the number and proportion of patients who are free of clinical spasms, and the proportion of patients with resolution of hypsarrhythmia at the end of the initial 2-week treatment phase, will be analyzed by treatment group using a chi-square test. However, if the number of patients in either of the treatment groups is less than 5 then a Fisher's exact test will be performed instead.

Changes in spasms and seizure subtypes during the initial 2-week treatment phase will be analyzed descriptively only.

The time to cessation of spasms during the initial 2-week treatment phase will be calculated as the number of days from first dose of IMP to the first day in which no spasms were recorded in the patient diary. Patients who do not have cessation of spasms by Visit 4 will be censored on the day of Visit 4. The time to cessation of spasms will be analyzed descriptively as well as with a log-rank test.

The CGIC and PGIC will be analyzed by treatment group using ordinal logistic regression, including treatment group as a factor and sex as a covariate in the model.

Safety and tolerability as determined by AEs, clinical laboratory tests, 12-lead electrocardiogram (ECG), physical examinations and vital signs.

Measurement where possible of plasma concentrations of CBD and its major metabolites (7-OH-CBD, 6-OH-CBD, and 7-COOH-CBD) will be investigated using a sparse sampling approach, with the aim to define a POPPK model.

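### The two key secondary endpoints, each compared with placebo at two doses, have no formal type I error control: about a 7–9% chance of a false result in favour of drug, against 2.5% for one test

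*Protocol*

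**What the plan says.** Protocol 4.1.2.1 marks two secondary endpoints as key: "Key: The number and proportion of patients who are free of clinical spasms" and "Key: The number and proportion of patients who have resolution of hypsarrhythmia", both read on video-EEG at the end of treatment. Together they make up the primary composite of Protocol 4.1.1.2.

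Protocol 13.6 says that in the pivotal phase "statistical hypothesis testing will be performed on the secondary endpoints as appropriate", and that "the major comparisons of interest are those between each of the GWP42003-P dose levels and placebo". Protocol 13.6.3.2 says that the two key endpoints "will be analyzed by treatment group using a chi-square test", with a switch to Fisher's exact test when a number of patients in a group is below 5.

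On error control, 13.6 limits the step-up Hochberg rule to the primary endpoint. Across endpoints it says that "no formal adjustment of statistical significance for multiple testing on multiple endpoints is required". The same sentence then asks that multiplicity be taken into account in interpreting secondary results. No order of testing, gate on the primary or division of alpha is given for the key secondaries. Protocol 13.6.2.2 leaves missing-data sensitivity analyses and rescue-medication handling to the SAP, but not multiplicity.

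The only significance level in Protocol section 13 apart from the Hochberg thresholds is in 13.1: "This is based on a 2-sided 5% significance level, based on a Fisher's exact test". It is not restated for secondary tests.

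**The concern.** A key secondary endpoint in a phase 3 trial is normally one on which the sponsor may want to make a claim. Here both are components of the composite, so they are the natural fallback if the composite fails. The primary has a decision rule that holds its two dose comparisons to 5% overall. The key secondaries have twice as many comparisons and no decision rule, and nothing makes their interpretation depend on the primary result. A favourable p-value on one component at one dose could be presented as a key finding with a higher false-positive risk than the primary carries.

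**Working it through.** **1. The protocol's own figure.** Hochberg with two tests has thresholds 0.05/1 = 0.050 when both pass and 0.05/2 = 0.025 when only one does. This matches 13.6. With a shared placebo arm, simulated familywise error for the primary is 4.8%, so the primary rule works as intended.

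**2. Inputs for the key secondaries.**
- Tests: 2 endpoints × 2 doses = 4 (4.1.2.1, 13.6).
- Arm size: 64, allocated 1:1:1 (13.1).
- Level: two-sided 5% per test. This is an assumption taken from 13.1.
- Null response rates: 10–25%, an assumption. The only placebo rate in the documents is 2 of 20 (10%) spasm-free after 5 days, in a background study (3.1).
- Correlation between the two endpoints: not given; 0 to 0.8 assumed.

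**3. Independence bound.** Either direction: 1 − 0.95⁴ = 1 − 0.8145 = 18.5%. In favour of drug: 1 − 0.975⁴ = 1 − 0.9037 = 9.6%. Independence cannot hold: the two doses share a placebo arm of equal size, so their test statistics correlate at 1/(1 + 1) = 0.5.

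**4. Shared placebo, normal approximation, no true effect.**

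| Endpoint correlation | Any p < 0.05, either direction | In favour of drug |
|---|---|---|
| 0 | 17.3% | 8.9% |
| 0.5 | 16.2% | 8.1% |
| 0.7 | 14.9% | 7.5% |
| 0.8 | 13.9% | 7.0% |

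**5. Binary data, 64 per arm, chi-square throughout.** With null rates of 10%/10%, 15%/20% and 25%/25% and latent correlation 0 to 0.8, the results are 15.3–17.7% in either direction and 7.5–8.9% in favour of drug.

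**6. Effect of the Fisher fallback.** The trigger in 13.6.3.2 can be read in several ways. At a 10% response rate on both endpoints, with correlation 0 to 0.7 on the response scale:

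| Reading of the trigger | Either direction | In favour of drug |
|---|---|---|
| Patients per group (64, so never triggered) | 17.5–15.1% | 8.7–7.3% |
| Expected count below 5 | 16.6–14.4% | 8.3–7.1% |
| Fewer than 5 responders in an arm | 9.2–8.0% | 4.7–4.1% |

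At 25% the responder reading makes no difference.

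**7. Key result without the primary.** Under the same null, with chi-square, a key endpoint favours drug at p < 0.05 while the primary fails at both doses in 5.9–8.7% of trials.

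**8. Candidate remedies under the same null.** Hochberg within each key endpoint alone leaves 9.4% to 7.6% in either direction, still above 5%. Hochberg across all four tests gives 4.7% to 4.0%. Gating the key endpoints behind the primary brings false key-secondary claims to 0.3% or less.

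**The case against.** A reader might infer a 15–18% chance of a false key-secondary claim. The documents do not support that. The figure counts results favouring placebo, whereas the success rule in 13.6 recognises only results in favour of drug, and the 18.5% upper bound needs an independence that the shared placebo rules out. The relevant figure is about half as large.

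A reader might also infer that the protocol would declare a component significant after the composite fails. It has no rule for declaring any secondary endpoint significant, and its caution about multiplicity suggests that these p-values are supportive. That softens the point but does not settle it: the caution gives no threshold, and the plan still tests endpoints it calls key.

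Other objections stand in part:
- The 5% level for secondaries is inferred. The Amendment 1 summary mentions 5% for all analyses, but it describes an earlier protocol version.
- The Fisher fallback matters. Read as responders, it roughly halves the error at a 10% response rate. At 5%, below the range assumed here, error in favour of drug would be 2.3–2.0%, no more than the nominal 2.5%.
- The key label is not idle. Protocol 13.6.2.2 uses it to count withdrawals and missing video-EEGs as non-response, so deleting the label would leave that rule without a referent.
- No analysis in the SAP is affected. SAP section 5 omits the pivotal phase, and SAP 4.2.1 plans no hypothesis testing.

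**Conclusion.** The concern holds as a gap in the protocol's pivotal design. The two key secondary endpoints at two doses have no formal type I error control, only a caution on interpretation. With no true effect, the chance of at least one false favourable key-secondary result is about 7–9%, roughly three times the 2.5% of a single test; in either direction it is about 15–17%. These figures rest on a two-sided 5% level, 64 per arm, chi-square tests, and assumed null rates of 10–25% and endpoint correlation of 0–0.8. At a 10% response rate under the responder reading of the Fisher trigger, the favourable figure is about 4–5%. The primary analysis is unaffected. This is an inexpensive improvement to make if the pivotal phase is run or its design reused.

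**What to change.** Add a short paragraph on serial gatekeeping to Protocol 13.6:

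- If both doses are significant on the primary, test spasm freedom with the same Hochberg rule at 0.05.
- If both doses are significant there too, test resolution of hypsarrhythmia in the same way.
- Stop at the first endpoint where either dose fails. A dose that passes at that endpoint keeps its result, but no later endpoint is tested formally.
- In all other cases, report the key-secondary p-values as nominal.

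Each endpoint is reached only after every earlier hypothesis has been rejected, so the primary keeps its full 5% and gives up nothing. Keep the key label, because 13.6.2.2 depends on it.

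The cost is one paragraph and one real restriction: no formal key-secondary claim when only one dose passes the primary. The SAP in its present scope needs no change.

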13.6.1 Evaluable Period

The start of the evaluable period (Day 1) is defined as the first day the patient took IMP in the trial or the day of randomization/initial assignment of IMP if this date is unknown. The end of the evaluable period for the pilot or pivotal phase is defined as the last day on which the study IMP was taken during the pilot or pivotal phase. The end of the evaluable period for the OLE phase is defined as the last day on which a study-related assessment was undertaken during the OLE phase as opposed to the last day on which the study IMP was taken. This is to allow data collected after discontinuation of the study IMP due to resolution of spasms to form part of the evaluable period.

13.6.2 Primary Endpoint(s)

13.6.2.1 Pilot Phase

The following endpoints will be analyzed descriptively only:

• Safety as determined by AEs, clinical laboratory tests, ECG, vital signs and physical examinations during the treatment period (see Section 13.6.5)

EudraCT Number: 2015-004904-50

Protocol V3 20Sep16

• The number and proportion of patients who are free of spasms and have resolution of hypsarrhythmia at the end of the 2-week treatment period, as determined by video-EEG.

13.6.2.2 Pivotal Phase

The number and proportion of patients who are free of spasms and have resolution of hypsarrhythmia at the end of the initial 2-week treatment phase, will be analyzed by treatment group using a chi-square test. However, if the number of patients in either of the treatment groups is less than 5 then a Fisher's exact test will be performed instead.

Patients who withdraw from the trial or patients who do not have a video EEG performed at the end of the 2-week treatment period will be included in the primary, and key secondary analyses as not being free of spasms and not having resolution of hypsarrhythmia.

Details of sensitivity analyses due to missing data and handling of patients potentially receiving rescue medication will be fully detailed in the SAP prior to unblinding.

13.6.2.3 Open-label Extension

To assess the long term safety as determined by AEs, clinical laboratory tests, ECG, vital signs and physical examinations during the treatment period (see Section 13.6.5).

13.6.3 Secondary Endpoint(s)

13.6.3.1 Pilot Phase

For the pilot phase, the following secondary endpoints will be analyzed descriptively only:

- The number and proportion of patients who are free of clinical spasms, as observed on video-EEG at the end of the treatment period.
- The number and proportion of patients who have resolution of hypsarrhythmia, as observed on video-EEG at the end of the treatment period.
- Changes in spasms and seizure subtypes by caregiver observation during the treatment period.
- Time to cessation of spasms during the treatment period, as determined by caregiver diaries.
- CGIC.
- PGIC.

EudraCT Number: 2015-004904-50

Protocol V3 20Sep16

Safety data is detailed in Section 13.6.5 below.

13.6.3.2 Pivotal Phase

For the pivotal phase, the number and proportion of patients who are free of clinical spasms, and the proportion of patients with resolution of hypsarrhythmia at the end of the initial 2-week treatment phase, will be analyzed by treatment group using a chi-square test. However, if the number of patients in either of the treatment groups is less than 5 then a Fisher's exact test will be performed instead.

Changes in spasms and seizure subtypes during the initial 2-week treatment phase will be analyzed descriptively only.

The time to cessation of spasms during the initial 2-week treatment phase will be calculated as the number of days from first dose of IMP to the first day in which no spasms were recorded in the patient diary. Patients who do not have cessation of spasms by Visit 4 will be censored on the day of Visit 4. The time to cessation of spasms will be analyzed descriptively as well as with a log-rank test.

The CGIC and PGIC will be analyzed by treatment group using ordinal logistic regression, including treatment group as a factor and sex as a covariate in the model.

Safety and tolerability as determined by AEs, clinical laboratory tests, 12-lead electrocardiogram (ECG), physical examinations and vital signs.

Measurement where possible of plasma concentrations of CBD and its major metabolites (7-OH-CBD, 6-OH-CBD, and 7-COOH-CBD) will be investigated using a sparse sampling approach, with the aim to define a POPPK model.

13.6.3.3 Open-label Extension

For the OLE phase, the following secondary endpoints will be analyzed descriptively only:

- The number and proportion of patients who are free of clinical spasms, as observed on video-EEG at the end of the treatment period.
- The number and proportion of patients who have resolution of hypsarrhythmia as, observed on video-EEG at the end of the treatment period.
- Changes in spasms and seizure subtypes by caregiver observation during the treatment period.
- Time to cessation of spasms during the treatment period, as determined by caregiver diaries.

EudraCT Number: 2015-004904-50

Protocol V3 20Sep16

- The number and proportion of patients who are free of spasms and have resolution of hypsarrhythmia, as determined by video-EEG after 3, 6, 9 and 12 months of treatment.
- The number and proportion of responders with relapse of spasms, and the time to relapse, as determined by caregiver diaries.
- Changes from baseline in length (height), body weight, and head circumference.
- CGIC.
- PGIC.
- Change from baseline in Vineland-II score.

Safety data is detailed in Section 13.6.5 below.

Measurement, where possible, of plasma concentrations of CBD and its major metabolites (7-OH-CBD, 6-OH-CBD, and 7-COOH-CBD) will be investigated using a sparse sampling approach, with the aim to define a POPPK model.

